### 2.3 Sample Size and Power

For all dose levels, from starting dose to the respective dose escalation levels, 3-6 patients will be enrolled and treated with CB-103 according to a staggered inclusion scheme to ensure adequate time for safety observation between inclusions, and before dose escalation. During the study, a minimum of 3 patients evaluable for the DDS will be treated per dose cohort until determination of the MTD or RP2D. Depending on the BLRM, additional patients may be enrolled in some dose cohorts. Approximately 11 dose cohorts are considered for this study with at least 3 patients per dose cohort. It is estimated that approximately 55 patients will be enrolled, not taking into account the drop-outs and additional patients enrolled for some of the dose groups. Based on the decision of the CRC, approximately 45 patients may be enrolled in the MTD/RP2D confirmatory cohort to confirm safety before opening Part B.

### 2.4 Interim Analyses

Each dose escalation step is considered to be an interim analysis. The BLRM will be updated with the respective number of patients treated and the number of DLTs observed in the last cohort. The updated model will then give a statistical recommendation for the next escalation step. However, a risk-benefit assessment that includes a comprehensive analysis of safety and available clinical information will be done to decide on the next escalation steps.

### 2.5 Primary Variable(s)

The primary endpoint for Phase I, Part A (dose-escalation) of this study is as follows:

- The number of patients experiencing dose-limiting toxicity (DLT) during the first 28-day cycle of CB-103 treatment

The primary endpoint for Phase I, Part A (confirmatory) of this study is as follows:

- The incidence rate, severity and relationship to CB-103 of adverse drug reactions and serious drug reactions according to common terminology criteria for adverse events (CTCAE) V4.03, safety laboratory, vital signs, ECG and ECHO/MUGA assessments.

### 2.6 Secondary Variable(s)

The secondary endpoints for Part A of this study are as follows, unless otherwise specified:

- The incidence rate, severity and relationship to CB-103 of adverse drug reactions and serious drug reactions according to common terminology criteria for adverse events (CTCAE) V4.03, safety laboratory, vital signs, ECG and ECHO/MUGA assessments in each dose group and expansion arm.
- CB-103 plasma concentrations, PK parameters:  $C_{max}$ ,  $t_{max}$ ,  $C_{min}$ ,  $C_{last}$ ,  $t_{last}$ , area under the curve (AUC) during 8 and 24 hours ( $AUC_{0-8}$ ,  $AUC_{0-24}$ ), AUC from time 0 extrapolated to infinite time ( $AUC_{0-\infty}$ ), apparent volume of distribution ( $V_d/F$ ), apparent volume of distribution at steady state ( $V_{ss}/F$ ), apparent clearance after oral administration ( $CL/F$ ),  $t_{1/2}$  and AR.
- To assess tumour response rates

- For solid tumour indications: to assess best overall response rate (CR + PR), assessed by RECIST 1.1 (Eisenhauer et al., 2009).
- For haematologic malignancies: to assess the best overall response rate (CR or CRi) per NCCN guidelines.
- To assess clinical benefit rate
  - For solid tumour indications: clinical benefit rate (CR + PR + SD), assessed by RECIST 1.1. (Eisenhauer et al., 2009).
- Duration of response (DOR), time to response, progression-free survival (PFS), OS.

## 2.7 Exploratory Variable(s)

The exploratory endpoints for Part A of this study are as follows:

- To assess plasma levels and PK parameters ( $C_{max}$ ,  $t_{max}$ ,  $C_{min}$ ,  $C_{last}$ ,  $t_{last}$ ,  $AUC_{0-8}$ ,  $AUC_{0-24}$ ,  $AUC_{0-\infty}$ ,  $t_{1/2}$  and AR) of metabolite(s) when feasible.
- To evaluate the relationship between CB-103 plasma concentrations and/or PK parameters (e.g.,  $C_{max}$  and  $AUC_{0-24}$ ) and safety, efficacy and PD parameters.
- To assess NOTCH and NOTCH target genes expression (NOTCH1-4 receptors, NOTCH ligands, NICD1-4 and NOTCH target genes) assessed by Nanostring expression analysis in pre- and post-treatment tumour tissue samples, whole blood / plasma samples and hair follicles in solid tumours and in T-lymphocytes from blood and/or bone marrow samples, whole blood and plasma in T-ALL/T-LBL, and assess their relation to clinical activity of CB-103.
- To assess the cerebrospinal fluid (CSF) exposure of CB-103 in haematological malignancies, in patients in whom IT prophylaxis is planned by the treating physician.
- To assess certain genotypes (e.g. cytochrome P450 enzymes or NAT) and assess relation to PK outcome data.
- To assess NOTCH genetic aberrations in pre- and post-treatment tumour tissue samples, whole blood and hair follicles in solid tumours and in T-lymphocytes from blood and/or bone marrow samples, whole blood and plasma in T-ALL/T-LBL, and assess their relation to clinical activity of CB-103.
- To assess NOTCH1-4 NICD expression assessed by IHC staining or by Western Blot in pre- and post-treatment in solid tumour tissue samples and to assess their relation to clinical activity of CB-103.
- To assess NOTCH mutations by genomic mutation analysis in tumour tissue samples in solid tumours and in T-lymphocytes from blood and/or bone marrow samples, whole blood and plasma in T-ALL/T-LBL, and to assess their relation to clinical activity of CB-103 treatment.
- To evaluate the intra-tumoral quantification of CB-103 in solid tumour tissue samples.
- To profile tumour tissue samples in solid tumours and T-lymphocytes from blood and/or bone marrow samples in T-ALL/T-LBL by single cell RNA-seq and/or other gene expression and genetic profiling techniques.
- To explore and assess changes in the immune system in pre- and post-CB-103 dosing whole blood and plasma (e.g., measure expression of cytokines/chemokines by RNA expression

analysis, quantify pro-inflammatory and anti-inflammatory cytokines and chemokines, phenotype different types of immune cells (T cells, B cells, dendritic cells and macrophages, etc.) using flow cytometry).

- To assess change from baseline cardiac intervals versus increasing plasma CB-103 concentrations.
- To assess the metabolic profile of CB-103 in biological matrices such as urine and/or stool samples based on metabolic expressions of CB-103 in urine and/or stool samples

## **2.8 Safety Variable(s)**

The safety variables of this study are as follows:

- Adverse events
- Laboratory findings
- Vital signs
- Physical examination and ECOG status
- Cardiac function

### 3. Analysis Populations

In accordance with ICH E3 and E9, the following analysis sets will be used for the analyses.

#### 3.1 Safety Set

The safety set will consist of all patients who received at least one dose of CB-103 and had at least one post-baseline safety assessment (where the statement that a patient had no adverse event on the Adverse Events eCRF constitutes a safety assessment). The safety set will be the primary population for all efficacy and safety related endpoints except determination of the dose-DLT relationship.

#### 3.2 Dose-Determining Set

The dose-determining set (DDS), which is the analysis set used for determination of the MTD, will consist of all patients in the safety set, who have (a) experienced DLT at any time during Cycle 1, and/or (b) met the minimum treatment and safety evaluation requirements without experiencing DLT within Cycle 1, as described below.

For all dose levels, from starting dose to the respective dose escalation levels, 3-6 patients will be enrolled and treated with CB-103 according to a staggered inclusion scheme to ensure adequate time for safety observation between inclusions, and before dose escalation. Depending on the BLRM, additional patients may be enrolled in some dose cohorts. The minimum treatment and safety evaluation requirements will have been met if, in Cycle 1, the patient has been treated with the planned dose of CB-103 for  $\geq 21$  days (75% of the planned dose; minimum exposure criterion), was observed for  $\geq 28$  days following the Cycle 1 Day 1 dose, and has completed the required safety evaluations for Cycle 1. Patients who do not meet these minimum treatment and safety evaluation requirements will be regarded as ineligible for inclusion in the DDS. Unless they experienced a DLT, patients will be replaced until the minimum number of 3 patients required for evaluation is reached.

The DDS will be used in the BLRM to estimate the dose-DLT relationship.

#### 3.3 PK Set

The PK set consists of all patients who have at least received one dose of study drug and have at least one post-dose PK measurement.

**Note:** Patients who were screened and have signed the informed consent but did not receive any treatment will be listed including reason for screen failure and any serious adverse event that is related to study procedure. These patients will not be part of any summary table except for summarizing disposition.

## **4. Data Handling**

### **4.1 Time Points and Visit Windows**

#### **4.1.1 General Definitions**

All assessment days will be related to the first day of first dose of treatment.

Day 1 is defined as first dose of treatment at Cycle 1 Day 1. Relative days after Day 1 are calculated as (assessment date – Day 1 date) + 1. Relative days prior to Day 1 are calculated as (assessment date – Day 1 date). The day prior to Day 1 is Day -1. Day 0 is not defined.

The date of the first dose of treatment for each subject will be taken from the PK sampling eCRF page.

The date of the last dose of treatment for each subject will be taken from the End of Treatment eCRF page. If the date in this eCRF page is missing, alternatively the date of End of Study will be used. If the date is missing because the subject was lost to follow-up, the date of the last visit will be imputed, if appropriate.

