### **Safety follow-up period**

All patients will have a safety follow-up for adverse events and serious adverse events 28 days after the last dose of CB-103 after which the end-of-study is reached. The safety follow-up visit must be performed by all patients who have received at least one administration of CB-103. All adverse events and/or serious adverse events occurring

during this period will be recorded in the Adverse Event electronic Case Report Form (eCRF).

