#### Phase I, Part A – Escalation:

- All patients from each dose cohort in Part A will stay overnight at the hospital for 1 night following their first CB-103 administration (C1D1) to allow for 24-hour PK sampling and ECG monitoring. During this time the patients will be closely monitored for safety. The overnight stays may not be required if reduced ECG and PK sampling is implemented.

In case CB-103 is given BID, one more overnight hospital stays at Day 8 in cycle 1 may be necessary to allow late samples collection.

- Patients will then undergo daily visits for 2 days following the overnight monitoring on Day 1 at the hospital, and will get their CB-103 doses administered in the hospital. Patients will stay at the hospital for at least 3 hours following each administration to allow safety reporting.
- Weekly visits to monitor safety and perform ECG monitoring and PK sampling are planned during the rest of the treatment period for the 1st cycle of CB-103 (28 days).
- Every 2 weeks visits to monitor safety and perform PK sampling are planned from cycle 2 until the completion of cycle 6.
- EOT visit within 14 days after the last dose of CB-103 (within the 6 cycles period).
- Safety follow-up visit (End-of-Study) for each patient within 28 days after the last dose of CB-103.
- Survival follow-up (e.g. per telephone) for 1 year is planned every three months after the End-of-study visit or after the last treatment cycle (if outside of the 6 cycles period).
- Further visits might be considered, depending on the health status of the patient, as determined by the treating Investigator of the respective investigational site.
- More frequent laboratory safety tests (e.g., to closely monitor the liver function), are possible and can be performed outside the study site for those patients leaving far away, if necessary. The laboratory reference ranges from the local laboratories must be collected, and filed in the laboratory report together with the patients' medical records. Care should be taken that any outliers possibly produced by the local laboratory findings are investigated at the study site.

Note: for those patients who may have the option to continue treatment after cycle 6, the subsequent visits are planned every 4 weeks if no medical issue or complication occurred in the previous cycles.

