### **4.2 Handling of Dropouts, Missing Data, and Outliers**

Missing, unused and spurious data will be dealt with as such.

Due to the dose escalation design of Part A of the study no missing imputation of missing values will be done for any analysis.

Currently no drop-outs are foreseen. However, if patients in the escalation phase (Part A) do not fulfil the minimum treatment and safety evaluation requirements and discontinue for a reason other than DLT they will be replaced.

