### Notes:

Duration of study treatment (months) is defined as:

$$(\text{date of last dose of study treatment} - \text{date of first dose} + 1) / 30.4375.$$

Actual exposure (months) is defined as:

$$\text{number of days when patients actually took study medication} / 30.4375.$$

Actual dose intensity (mg/d) is defined as:

$$\text{total actual dose taken (mg)} / \text{actual exposure (d)}.$$

Planned dose intensity (mg/d) is defined as:

$$\text{total planned dose taken (mg)} / \text{planned exposure, i.e. planned days on treatment (d)}$$

Relative dose intensity is defined as:

$$\text{actual dose intensity} / \text{planned dose intensity} \times 100\%$$

Treatment compliance (in %) is defined as:

$$\text{total actual dose taken} / \text{total planned dose} * 100$$

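### SAP 4.1.1 fills a missing last-dose date with the End of Study date, which can count up to 28 off-drug days as treatment.

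*SAP*

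**What the plan says.** SAP 4.1.1 sets three rules for the last-dose date, in this order.

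- Primary source: "The date of the last dose of treatment for each subject will be taken from the End of Treatment eCRF page".
- Fallback: "If the date in this eCRF page is missing, alternatively the date of End of Study will be used". Nothing is subtracted for the follow-up interval.
- Loss to follow-up: "If the date is missing because the subject was lost to follow-up, the date of the last visit will be imputed, if appropriate".

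The protocol places a patient's End of Study at the safety follow-up. Section 5.1.1.1 describes a "safety follow-up for adverse events and serious adverse events 28 days after the last dose of CB-103 after which the end-of-study is reached". Section 8.1, for Part A escalation, has "Safety follow-up visit (End-of-Study) for each patient within 28 days after the last dose of CB-103". Protocol Appendix 1 and SAP Appendix 3 label the safety follow-up column EOS-A and, in their footnotes, also use the 'within 28 days' wording.

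The date is used in two SAP definitions. The Treatment Period (SAP 4.1.3) ends at the last dose. Under SAP 5.5, "Duration of study treatment (months) is defined as" the last-dose date minus the first-dose date plus 1, divided by 30.4375. SAP 4.2 states that "no missing imputation of missing values will be done for any analysis".

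**The concern.** By design, the End of Study date falls after dosing has stopped. Using it unadjusted as the last-dose date counts the off-drug follow-up interval as time on treatment. For a patient who completes follow-up, the error always runs towards longer treatment.

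What is at stake is a descriptive output, treatment duration by cohort. Escalation cohorts are planned at 3 to 6 patients, so a single affected patient can move a cohort summary visibly.

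The fallback also passes over closer information that the trial already collects. Protocol 7.4 has actual dosing times transferred from the diary to the eCRF, and doses and dose changes entered on eCRF forms. SAP 5.5 itself relies on day-level dosing data, because it counts the days on which drug was actually taken. If those days can be counted, the last of them can be identified.

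**Working it through.** **Inputs**

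- Duration in months = (last dose − first dose + 1) / 30.4375 (SAP 5.5).
- Compliance = total actual dose / total planned dose × 100 (SAP 5.5).
- End of Study lag: 28 days after the last dose (protocol 5.1.1.1), or within 28 days (protocol 8.1; footnotes to protocol Appendix 1 and SAP Appendix 3). Lags of 14 and 7 days are assumed, to show a range.
- EOT visit: within 14 days after the last dose (protocol 5.1.1.1).

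The plan gives no figure of its own to reproduce, and no rate of missing EOT-page dates.

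**Effect on duration.** Moving the last-dose date later by L days adds L / 30.4375 months, however long the patient was treated:

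- L = 28: 28 / 30.4375 = 0.92 months
- L = 14: 14 / 30.4375 = 0.46 months
- L = 7: 7 / 30.4375 = 0.23 months

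| Days on drug | True duration (months) | 28-day lag | 14-day lag | 7-day lag |
|---|---|---|---|---|
| 28 (1 cycle) | 0.92 | 1.84 (+100%) | 1.38 (+50%) | 1.15 (+25%) |
| 56 (2 cycles) | 1.84 | 2.76 (+50%) | 2.30 (+25%) | 2.07 (+12.5%) |
| 84 (3 cycles) | 2.76 | 3.68 (+33%) | 3.22 (+17%) | 2.99 (+8%) |
| 168 (6 cycles) | 5.52 | 6.44 (+17%) | 5.98 (+8%) | 5.75 (+4%) |

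One affected patient at the full 28 days moves a cohort mean by 0.92 / 3 = 0.31 months with 3 patients, or 0.92 / 6 = 0.15 months with 6.

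**Effect on compliance, under an assumption.** SAP 5.5 does not say which date ends the planned days. Suppose that they run to the imputed date, the daily dose is constant and no dose is missed. A patient dosed for d days, whose true compliance is 100%, then shows d / (d + L):

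| Days on drug | 28-day lag | 14-day lag | 7-day lag |
|---|---|---|---|
| 28 | 50.0% | 66.7% | 80.0% |
| 56 | 66.7% | 80.0% | 88.9% |
| 84 | 75.0% | 85.7% | 92.3% |
| 168 | 85.7% | 92.3% | 96.0% |

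If planned dose is counted only to the true last dose, or taken from dosing records, the effect is zero.

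**What does not use this date**

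- Actual exposure and actual dose intensity are built on days on which drug was taken.
- Relative dose intensity is unchanged if planned dose and planned days cover the same period.
- Treatment-emergent status (SAP 5.7.1) depends on the first dose, with no upper limit at the last dose.
- DLTs are counted over 28 days from the first dose. The minimum-exposure rule for the dose-determining set counts treated days in Cycle 1.

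**With a closer fallback.** The EOT visit date is at most 14 days late, so its error is at most 0.46 months, against up to 0.92 months for End of Study. The last recorded intake date has no error if the dosing record is complete.

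**The case against.** The strongest reply is that the rule will seldom be used and does little when it is. Every patient is required to attend an EOT visit, and protocol 8.11.1.1 asks for an EOT eCRF giving the date and reason for stopping. Data are checked and cleaned before lock. Loss to follow-up, an obvious cause of a missing date, has its own rule. All of this stands. It limits the importance of the point, but the fallback still gives a wrong date for a patient who completed follow-up.

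Four stronger readings are tempting, and the documents do not support them.

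- **Every affected patient gains 28 days.** Several places say within 28 days. A patient who dies or withdraws consent may have an End of Study date close to the last dose, and the documents do not define that date for such patients. So 28 days is the upper figure.
- **Compliance will be understated.** That needs planned days to run to the imputed date, which SAP 5.5 leaves undefined.
- **Safety conclusions shift through the Treatment Period.** No SAP safety analysis was found that uses that period as a window. The protocol's summary of deaths within 28 days of the last dose (10.6.1.1) would be sensitive to the date, but SAP 5.7.1 plans only a summary of all deaths.
- **The fallback flatly contradicts SAP 4.2.** The SAP also has conventions for missing medication start dates (5.4.2), missing adverse event start dates (5.7.1) and concentrations below the quantification limit (5.8.2). The sentence in 4.2 is better read as too broad than as aimed at this rule.

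**Conclusion.** The rule is wrong as written, on a small scale. If the EOT-page date is missing, loss to follow-up is not the reason and the patient completed follow-up, SAP 4.1.1 adds off-drug time to the Treatment Period and to treatment duration. The addition is up to 28 days (0.92 months), 0.46 months at a 14-day lag and 0.23 months at 7 days.

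These sizes rest on End of Study being the safety follow-up visit, as the protocol and the SAP schedule have it. The 14-day and 7-day lags are illustrative. The number of affected patients cannot be estimated from the documents and may be zero.

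An effect on compliance is possible but not established. A reader might also infer that the dose-finding result is at risk. It is not, because the DLT and MTD analyses do not use the last-dose date.

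**What to change.** In SAP 4.1.1, delete the End of Study fallback and replace it with this order:

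1. If the EOT-page date is missing, use the last CB-103 intake date in the eCRF dosing records.
2. If there is none, use the EOT visit date as an upper bound and flag the patient as having an imputed date.

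The separate rule for loss to follow-up can stay.

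Two short clarifications should go with it. In SAP 5.5, state which end date bounds the planned days behind planned dose intensity and compliance. In SAP 4.2, say that the no-imputation statement does not cover the date conventions listed elsewhere in the SAP.

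The cost is a few sentences in the SAP, one changed derivation and a flag in the listings. No new data are needed.

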#### **4.1.2 Baseline Period**

For all subjects, the baseline period is defined as the period from informed consent to the first dose of treatment. For some variables, data from more than one assessment within the baseline Period can be collected prior to the first dose of treatment.

The baseline value for a variable is therefore defined as the last non-missing value collected before the first dose of treatment in the baseline period.

#### **4.1.3 Treatment Period**

The Treatment Period is defined as the period from the date / time of the first dose of treatment up to and including the date / time of the last dose of treatment.

#### **4.1.4 Visit Windows**

All data will be analyzed using nominal study visit as defined in the Study Schedule and eCRF. No visit windows will be applied for summary and analysis.

### **4.2 Handling of Dropouts, Missing Data, and Outliers**

Missing, unused and spurious data will be dealt with as such.

Due to the dose escalation design of Part A of the study no missing imputation of missing values will be done for any analysis.

Currently no drop-outs are foreseen. However, if patients in the escalation phase (Part A) do not fulfil the minimum treatment and safety evaluation requirements and discontinue for a reason other than DLT they will be replaced.

## 5. Statistical Methods

### 5.1 General Principles

All data processing, summarization and analyses will be performed using Labcorp Drug Development's SAS Environment / Version 9.4 (or later) of the SAS® statistical software package. Baseline, safety and tolerability as well as efficacy analyses will be based on the SS.

Pharmacokinetic evaluation will be done for the PK set.

The dose-determining analyses, i.e. those to determine MTD or RP2D, will be done for the DDS.

Results will be listed and summarized using descriptive statistics overall and by cohort:

- All patients
- Cohort 1 (dosing level 1, e.g. 15mg)
- Cohort 2 (dosing level 2, e.g. 30mg)
- Etc.
- Cohort with RP2D

All summary statistics will be rounded (using the SAS® function ROUND) and presented to one more decimal place than the raw value, except for the minimum and maximum values that will be presented with the same decimal precision as the raw value.

For qualitative variables, the number (n) and percentage (%) of subjects with non-missing data per category will be the default summary presentation, and where appropriate and present, the number of missing values as a "Missing" category. Number of subjects in the analysis population will be used as denominator for percentages calculation, unless stated otherwise in TFLs mock shell(s).

When appropriate, considering number of patients within groups, Clopper-Pearson confidence intervals (CI) will be provided for rates.

For time to event type data, Kaplan-Meier estimates will be presented for dose groups with sufficiently high patient numbers.

Due to being of non-comparative nature, no inferential statistical analysis will be applied in either the escalation or the expansion part of this study to compare dose groups or arms.

The final statistical analysis will occur after all patients have discontinued treatment for any reason and completed safety FU.

All additional data collected during long-term survival FU will be separately reported in a combined FU analysis.

